4.3 Other variables and covariates

4.3.1 Baseline characteristics

Baseline information consists of :

Demography:

Age, sex, race, ethnicity,

Vital signs:

Weight, height, BMI

Smoking history:

Never, current, former usage, number of pack years

Surgical History:

Surgical history will be coded using MedDRA codes of the version currently in effect at the time of database lock. The number (percentage) of patients reporting a surgical history will be summarized by system organ class and preferred term.

Cancer Therapy – Osimertinib:

Duration of Osimertinib treatment, dose, dose adjustment, cause of dose adjustment, dose interruption, cause of dose interruption, dose termination, cause of dose termination, best response.

ECOG Performance Status:

Normal activity, restricted activity, in bed less than or equal to 50% of the time, in bed more than 50% of the time, 100% bedridden, death.

Pathology At Time of Diagnosis:

Histology type, primary tumour, regional lymph nodes, distant metastases.

Extent of Disease At Time of Diagnosis:

Metastatic/Locally Advanced, location, tumor number

Pathology Upon Entry to Study:

Histology type, primary tumour, regional lymph nodes, distant metastases.

Extent of Disease Upon Entry to Study:

Metastatic/Locally Advanced, location, tumor number

Multi Gene Status At Time of Diagnosis:

Sample type, test type, gene name and variant classification

Medical history:

Medical history will be coded using MedDRA codes of the version currently in effect at the time of database lock. The number (percentage) of patients reporting a medical history will be summarized by system organ class and preferred term.

Nicotine Use

Classification and pack years

5. ANALYSIS METHODS

5.1 General Aspects

All statistical analyses will be completed using SAS version 9.4 or later, and R 4.0 or later. Descriptive statistics will be provided for all variables, as appropriate. Continuous variables will be summarized by the number of observations, mean, standard deviation, median, interquartile range (Q1, Q3), minimum, and maximum. Categorical variables will be summarized by frequency counts and percentages for each category. The 95% confidence interval (CI) will be calculated as appropriate.

The analyses will be based on Full analysis set (FAS), which will include all patients who meet the required inclusion/exclusion criteria and have valid Gene data from both plasma and tissue.

Patients missing tissue or plasma NGS data or MET data will not be used for concordance analysis, but only for individual tissue or plasma analysis.

5.1.1 Handling of Missing Data

Missing data will not be imputed unless otherwise specified elsewhere in the SAP.

5.2 Subject disposition

The subject disposition will be summarized. Screened, enrolled, screen failure, study completion, study discontinuation will be summarized and the reasons for failure and study discontinuation will be listed.

5.3 Baseline characteristics

Analysis will be performed based on FAS.

Descriptive statistics will be provided for all variables, as appropriate.

Baseline information consists of demography(age, sex, race, ethnicity, weight, height, BMI), smoking history , medical history, ECOG/WHO performance status, histology, clinical stage with lymph node and distant metastasis at diagnosis and post 1L Osimertinib, duration of 1L Osimertinib treatment, best response of 1L Osimertinib.

Age will be divided to two categories: <65 years, >= 65 years.

Duration of Osimertinib treatment:

If date is complete, then Duration of Osimertinib treatment (Months) = (End Date – Start Date)/365.25*12, keep one decimal places.

If either day of start date or end date is missing, then Duration of Osimertinib treatment (Months) = (Year of End Date – Year of Start Date)*12 + (Month of End Date – Month of Start Date), where the Year and Month of Start Date and End Date will be extracted from the corresponding date.

If missing day and month, then Duration of Osimertinib treatment (Months) will be considered as missing.

5.4 Biomarker analysis

5.4.1 Primary Endpoint

The primary objective is to describe the gene profile in EGFRm advanced NSCLC patients after progression on 1L Osimertinib treatment.

Gene profile in tissue will be analyzed by NGS method. All gene alterations in tissue(e.g., gene mutation, amplification, deletion, fusion, etc.) detected by NGS will be observed.

Proportion of Gene X alteration(%) = (number of patients with Gene X alteration, which is an example of a certain gene)/(total number of patients in the FAS)×100%. Some cases which patients have more than one gene alteration need to be considered, therefore percentages may not add up to 100%.

The OncoPrint plot will be used to visualize the gene alterations across all cases and reveal trends, such as co-occurrence and mutual exclusivity.

5.4.2 Secondary Endpoint

The secondary objective is to assess gene profile in plasma, concordance of plasma and tissue and the percentage of pathology transformation will be analysed by NGS method and IHC. All gene alterations in plasma(e.g., gene mutation, amplification, deletion, fusion, etc.) detected will be observed. Proportion of Gene X alteration(%) = (number of patients with Gene X alteration, which is an example of a certain gene)/(total number of patients in the FAS)×100%. Some cases which patients have more than one gene alteration need to be considered, therefore percentages may not add up to 100%.

Using selected representative genes to measure the concordance. The representative genes should include the top 20 mutated genes observed in tissue samples. Concordance of Gene X in plasma and tissue is defined as sensitivity, specificity, positive predictive value (PPV), negative predictive value (NPV), and overall percent agreement between plasma and tissue results., Tissue sample is the reference standard.

Sensitivity=(number of patients with positive result in both plasma and tissue)/(total number of patients with positive result in tissue samples)×100%;

Specificity=(number of patients with negative result in both plasma and tissue)/(total number of patients with negative result in tissue samples)×100%.

[figure not shown]
PPV (%)=(number of patients with positive result in both plasma and tissue)/(total number of patients with positive result in plasma samples)×100%;

NPV (%)=(number of patients with negative result in both plasma and tissue)/(total number of patients with negative result in plasma samples)×100%.

Overall percent agreement(%) =(number of patients with same result <positive or negative> in both plasma and tissue)/(total number of patients in FAS)×100%

Pathology transformation defines as pathological type of lung cancer change, which will be confirmed by pathologists. Number and percentage of patients with pathology transformation will be summarized. Proportion of pathology transformation(%) = (number of patients with pathology transformation)/(total number of patients in the FAS)×100%.

CCI

CCI

[REDACTED]

[REDACTED]
[REDACTED]
[REDACTED]

[REDACTED]

[figure not shown]
		[REDACTED] [REDACTED]	[REDACTED]	
[REDACTED]	[REDACTED]			
	[REDACTED]			
[REDACTED]				

[REDACTED]
[REDACTED]
[REDACTED]
[REDACTED]
[REDACTED]
[REDACTED]

[REDACTED]
[REDACTED]
[REDACTED]
[REDACTED]
[REDACTED]
[REDACTED]
[REDACTED]
[REDACTED]

CCI

CCI

■

■

■

■

■

[figure not shown]

■

□. TIMING OF ALL ANALYSES

Two analyses are planned. The first interim analysis data cut-off (DCO) point will happen when approximately 100 patients have completed their gene testing in tissue and whole blood and got their testing results. The first interim analysis will focus on the primary outcome and secondary outcomes. The final analysis is planned when the last patient has completed their gene testing in tissue and whole blood and got their testing results. The primary outcome, secondary outcomes CCI

will be updated using the data of all patients.

□. CHANGES TO PROTOCOL PLANNED ANALYSES

Changes to protocol planned analyses are summarized as following:

- Added overall percent agreement as a measurement of concordance of NGS in tissue and plasma for secondary endpoint analysis.

□. APPENDIX

□.1 Schedule of Activities

Table 1 Schedule of Activities

Procedure	Screening and Data Collection	Notes	Details in CSP Section or Appendix
Visit	1		
Informed consent ^a	X		Sections 5.1
Inclusion and exclusion criteria	X		Section 5.1 and 5.2
Histology	X		
Clinical stage with lymph node and distant metastasis at diagnosis and post 1L Osimertinib	X		
Record documented common EGFR mutation results by an accredited laboratory through ARMS, Super-ARMS, and NGS testing ^b	X		
Demography and smoking history ^c	X		Section 7.2.1
Physical examination and weight(Kgs)	X		Section 7.2.1
Height(CMs)	X		Section 7.2.1
Medical history and comorbid conditions ^d	X		Section 5.1 and 5.2
WHO/ECOG performance status post Osimertinib 1L treatment	X		Section 7.2.2

Duration of 1L Osimertinib treatment ^e	X		
Best response of 1L Osimertinib	X		
Progression pattern post 1L Osimertinib	X		
Mandatory screening tumour tissue sample (archived or newly acquired biopsy) for Central NGS testing and central MET FISH testing; local IHC testing (included MET overexpression by MET IHC and SCLC pathology transformation by IHC)	X		Section 7.3.1
Mandatory screening blood sample (newly acquired; 2*10ml) for Central NGS testing and central ddPCR MET amplification testing	X		Section 7.3.1 and Appendix C

a Written informed consent and any locally required privacy act document authorisation must be obtained prior to performing any protocol-specific procedures, including screening/baseline evaluations.

b Participants are eligible to be considered for inclusion on the basis of local pre-existing EGFR tumour tissue or plasma testing results by molecular testing.

c Include date of birth or age, gender, race, and ethnicity for all participants.

d Include any treatment history before enrolling the study, complication and related history (chronic diseases which require treatment currently).

e Include the start and end dates of 1L Osimertinib treatment; starting dose,

Note: Data collection following study analysis until the end of the study is described in Section 7.

Note: The screening visit will confirm that the patients will be receiving a biopsy (scheduled for after enrolment), but they will not actually receive a biopsy at the screening visit.

CSP=Clinical Study Protocol; ECOG=Eastern Cooperative Oncology Group; ICF=informed consent form; WHO=World Health Organisation

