Currently, analysis of circulating tumor DNA(ctDNA) has been the predominant method to investigate acquired resistance mechanisms, but non-genetic mechanisms of resistance, including histologic transformation and protein expression change cannot be captured by plasma NGS analysis. Compared to tissue analysis, sensitivity for copy number changes and chromosomal rearrangements using plasma samples is instable[3, 4, 19-23]. ddPCR is as technique with high sensitivity and specificity, which is widely used for the absolute quantification of nucleic acid through Poisson distribution [24] and also as an alternative technique for MET amplification testing in plasma samples has been explored in some previous studies. Kitazono et al. have attempted to use ddPCR to detect MET amplification in three blood samples of NSCLC patients with EGFR-TKI resistance and proved its feasibility at the first time [25]. The recent study further explored the performance of MET amplification testing by ddPCR in tissues and paired peripheral blood samples from advanced NSCLC patients who had progressed on EGFR-TKI[26]. A total of tissues and the paired peripheral blood samples from 103 advanced NSCLC patients who had progressed on EGFR-TKI were collected for MET amplification testing by using ddPCR. In parallel, MET amplification was verified by FISH in tissue samples. The concordance rate of MET amplification in tissue samples between ddPCR and FISH was 100% (102/102), and it was 94.17% (97/103) by ddPCR testing between tissue and paired and peripheral blood samples with performance of sensitivity 66.67% and specificity 98.86%. Therefore, ddPCR is an potentially alternative method for MET amplification testing in both tissues and peripheral blood samples, which is worthy of exploring and validating in more studies (appendix H).

Thus, this study plans to use paired tumor tissue and whole blood to detect molecular and histologic mechanisms of resistance to 1L Osimertinib and to assess the concordance of plasma and tissue. And these paired tissue and blood samples are also used to assess the concordance of MET amplification between FISH and ddPCR testing as exploratory endpoints. Additional, the prevalence of MET amplification by FISH testing and MET overexpression by IHC testing, and the overlap ratio of prevalence between MET amplification and MET overexpression are also as exploratory endpoints in this study.

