**NGS raw data Process:**

1. Filter out low quality reads from raw data by NCfilter.
2. The clean reads were aligned to the human genome build hs37d5 using sentieon bwa software. Subsequent BAM files were further processed for deduplication, base quality recalibration, and indel realignment using sentieon software.
3. Data quality control was performed using NCbamInfo from the final BAM files.
4. Somatic single nucleotide variants (SNVs) and somatic small insertions and deletions (Indels) were called using realDcaller and sentieon TNScope, respectively. The candidate somatic SNVs

and indels were annotated, and reviewed by BedAnno and HChot software. A series of designed filter rules were subsequently applied to filter out false positive sites.

5. Somatic structural variants (SV) were identified, annotated and filtered by NCsv, annosv, and filtersv software, respectively.

6. Gene-level copy number variations (CNVs) were calculated by using CNVKit. Annocnv and filtercnv software were used for subsequent annotation and filterititon.

All final candidate variants were manually verified with the integrative genomics viewer browser.

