**Table 13 Validation information of plasma sample detected by ddPCR**

Sample type	Plasma
-------------	--------

Sample requirement	1. non- hemolysis 2. extraction DNA $\geq 0.5$ ng/ $\mu$ l 3. total DNA content $\geq 25$ ng
Assay	MET gene amplification testing assay -ddPCR
Cut off	MET/CEP7 $\geq 2$

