3. ANALYSIS SETS

3.1 Definition of analysis sets

The following populations are defined:

Table 1 Populations for Analysis

Population/Analysis Set	Description
Enrolled	All participants who sign the ICF
FAS	All participants who meet the required inclusion/exclusion criteria and have valid Gene data from both plasma and tissue. CCI

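### Plasma-tissue concordance is planned per gene without separating amplification from mutation, although the plasma assay's limits for the two differ widely

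*SAP*

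**What the plan says.** SAP 5.4.2 defines the plasma gene profile over all alteration types together: "All gene alterations in plasma(e.g., gene mutation, amplification, deletion, fusion, etc.) detected will be observed". The proportion is patients with a Gene X alteration over the FAS. Concordance is then defined for Gene X, with tissue as reference, for representative genes that should include the 20 most often mutated in tissue. Each result has two categories; overall agreement counts the "number of patients with same result <positive or negative> in both plasma and tissue". MET is named as a representative gene in the SAP objectives table and in SAP 4.2.3.

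The FAS requires patients to "have valid Gene data from both plasma and tissue", and valid is not defined in the visible text. The only visible exclusion from concordance is for absent results: "Patients missing tissue or plasma NGS data or MET data will not be used for concordance analysis".

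Protocol 4.2.1 gives the reading rule: if the point estimate of sensitivity is at least 80%, plasma is taken as consistent with tissue for NGS.

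Protocol Appendix F gives the limits. Plasma NGS (Table 10): 0.5% for hot-spot and 1.0% for other mutations, 3.2 copies for gains. Tissue NGS (Table 9): 3.8 copies, with at least 20% tumour content required. No minimum tumour DNA is stated for plasma. The pipeline summary says "Gene-level copy number variations (CNVs) were calculated by using CNVKit", followed by annotation and filtering, and mentions no tumour-fraction correction. Protocol 2.2 itself warns that "sensitivity for copy number changes and chromosomal rearrangements using plasma samples is instable".

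**The concern.** A mutation and a copy gain in the same gene are different detection problems in plasma. A mutation is read as an allele fraction, and a small share of tumour DNA is enough. A gain is read as an average over tumour and normal DNA, so normal DNA pulls the reading towards two copies.

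If one gene row pools both, three things follow:

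- The pooled sensitivity depends on the mix of alteration types in that gene as well as on how well plasma works.
- A row can reach 80% on the strength of its mutations while most amplifications are missed.
- A patient with a MET mutation in tissue and a MET amplification in plasma is positive in both samples and counts towards sensitivity, PPV and overall agreement, although the two tests found different things.

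The protocol calls MET amplification a key resistance mechanism, so this is the gene where a reader is most likely to use the row to decide whether plasma will do.

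**Working it through.** **1. The protocol's own blood figure, and what pooling does to it.** Protocol 2.2 reports "sensitivity 66.67% and specificity 98.86"% for MET by ddPCR in blood against tissue. Appendix H, Table B reproduces this: (4 + 6)/(9 + 6) = 10/15 = 66.67%; 87/88 = 98.86%; overall 97/103 = 94.17%. The 66.67% is reached only if polysomy counts as positive with amplification. For amplification alone it is 4/9 = 44.4% (exact 95% CI 13.7% to 78.8%). This is a different assay from the study's NGS, but it shows in the protocol's own data how merging classes changes the answer.

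**2. Tumour DNA needed for a plasma NGS copy-number call.** Inputs: limit 3.2 copies (Table 10); 10 tumour copies, the minimum of the FISH cut-off in Table 12; 5 and 20 copies for range. Assumptions: diploid normal DNA, and a limit that applies to the uncorrected reading. With C tumour copies and tumour share f:

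reading = 2 + (C − 2)f, so f needed = (3.2 − 2)/(C − 2)

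| Tumour copies | f needed |
|---|---|
| 5 | 1.2/3 = 40% |
| 10 | 1.2/8 = 15% |
| 20 | 1.2/18 = 7% |

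At f = 5% a 10-copy tumour reads 2 + 8 × 0.05 = 2.4 copies, which is below the limit.

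**3. Hot-spot mutation.** Limit 0.5% allele fraction. For a heterozygous mutation, allele fraction = f/2, so f needed = 1%. At 10 copies the gap is 15/1, about 15-fold.

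**4. Tissue NGS under the same model.** At the permitted 20% tumour content a 10-copy tumour reads 2 + 8 × 0.20 = 3.6, below the 3.8 limit. It needs 1.8/8 = 22.5% tumour content. The reference standard can therefore miss gains too.

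**5. How far a pooled row can mask this.** As an illustration only, borrow 4/9 for amplification and take the limiting case in which every mutation is found. If amplifications are a share w of a gene's tissue positives, pooled sensitivity = 1 − (5/9)w. It stays at or above 80% while w ≤ 0.20/(5/9) = 36%. A row could meet the 80% reading with more than half of its amplifications missed.

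**The case against.** The strongest reply is that the all-comer analysis is already right. Protocol 4.2.1 asks whether plasma can stand in for tissue when a biopsy is not possible, and low shedding of tumour DNA is part of that answer. This stands. A reader might infer that undetected amplifications are scored as true negatives, or that the substitution question is answered wrongly for MET. Neither follows: tissue is the reference, so a tissue-amplified, plasma-negative patient is a false negative and lowers both sensitivity and NPV.

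Second, the pooled MET row is a reading of the text. SAP 5.4.2 names no gene, and SAP 4.2.3 speaks of plasma and tissue mutation for each gene. This stands in part. The SAP does not define a positive result for concordance. If amplification counts, it is pooled with mutation. If only mutations count, plasma detection of amplification gets no NGS concordance result. Either way the text needs settling.

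Third, the 3.2-copy limit may already be corrected for tumour fraction, since the filtering rules are not described. That cannot be excluded, so the tumour-fraction figures are conditional.

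Fourth, the ddPCR cut-off (MET/CEP7 of at least 2, Table 13) raises the same issue. The same model gives 2/8 = 25% tumour DNA for 10 copies with two CEP7 copies in the tumour. But the quoted SAP sentence concerns plasma NGS, and the exploratory analysis text is blacked out, so its handling of ddPCR negatives cannot be judged or called missing. The 15% and 25% figures belong to two assays and are not a range for one quantity.

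Last, Appendix H does not prove dilution. It gives no tumour fractions, 4/9 is imprecise, and blood matched tissue in all 6 polysomy cases.

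**Conclusion.** The point holds as one about reporting. The visible SAP gives one concordance row per gene with no separation of alteration class, while Table 10 sets limits that, under the stated assumptions, differ about 15-fold in the tumour DNA needed at 10 copies (about 7-fold at 20, 40-fold at 5). The assumptions are an uncorrected copy reading, a diploid background and a heterozygous hot-spot mutation. The masking and the false agreement in a pooled row do not depend on the exact fold, only on plasma detecting the two classes unequally, which Protocol 2.2 itself suggests.

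A reader might go further in two ways that the documents do not support. One is to call the plasma MET amplification frequency a lower bound: Table 10 states specificity only as above 95%, so false positives could approach 5%, against cited MET amplification rates of 7% and 15%. Likely underestimate when tumour DNA is low is as far as the text goes. The other is to set fixed allele-fraction cut-points, such as 7.5% for half of 15%: these need a heterozygous EGFR founder mutation. If the mutant allele held 6 of 7 EGFR copies, then 6f/(2 + 5f) = 7.5% gives f = 0.15/5.625, about 2.7% tumour DNA instead of 15%.

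**What to change.** In SAP 5.4.2:

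- Keep the all-comer tables and define a positive result for concordance.
- For each representative gene with both classes, MET in particular, give sensitivity, specificity, PPV, NPV and overall agreement separately for amplification and for mutation. Apply the 80% reading of Protocol 4.2.1 to each class.
- As a descriptive supplement, show plasma MET amplification results against the patient's founder EGFR plasma allele fraction, without cut-points.
- Note beside the plasma MET amplification frequency that it is likely an underestimate when tumour DNA is low.
- State that tissue NGS is also subject to dilution, so discordance is not put down to plasma alone.
- Extend this to ddPCR only if the blacked-out text does not already cover it.

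The cost is SAP wording, extra rows and one display. No new sample or assay should be needed, since the data come from the NGS runs already planned. The drawback is precision. At the cited 7% to 15%, 180 patients give 0.07 × 180 = 13 to 0.15 × 180 = 27 MET-amplified cases. With 20 of them, an observed 16/20 = 80% has an exact 95% CI of 56% to 94%. EGFR copy gain also makes allele fraction only a rough guide to tumour fraction.

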While similar to 1/2 G *EGFR*-TKI, acquired resistance to Osimertinib invariably often develops with a median PFS of 19 months[1]. The characterization of the landscape of resistance enables the development of subsequent therapies, but mechanisms of resistance to Osimertinib is primarily derived from patients who received Osimertinib after other *EGFR*-TKIs, such as *EGFR* C797, *EGFR* G724, *EGFR* L792, *MET* amplification, and so on[2-5]. Prior reports of acquired resistance mechanisms to Osimertinib primarily focus on patients who received Osimertinib as the second-line treatment. However, the mechanisms of resistance to Osimertinib in the first-line treatment are far from being clearly explored. As Osimertinib in the first-line treatment is applied more and more widely in advanced *EGFR*m+ NSCLC patients, we urgently need to know the resistance mechanisms to guide subsequent treatment strategy. Until now, the largest study to explore acquired resistance mechanism to 1L Osimertinib was FLAURA study, which detected 91 paired plasma samples by next generation sequencing (NGS) . The most common acquired resistance mechanisms were *MET* amplification (15%) and *EGFR* C797X mutation (7%)[6]. The result was quite different from the study conducted by Adam J. Schoenfeld et al using tissue (N=27), with squamous transformation accounting for 15% and *MET* amplification 7%[7]. The reason for different results maybe because these two studies used different samples to analyse resistance mechanisms, and the above two detection methods may have different sensitivity and specificity. In addition, Schoenfeld et al study was limited to patients at one site, Memorial Sloan Kettering Cancer Center in NY, USA.

Although some small sample studies have reported the possible resistance mechanisms of Osimertinib in the first-line treatment, it is still an urgent need to explore the whole gene profile

in *EGFR*m advanced NSCLC patients post Osimertinib 1L treatment by paired tissue and plasma to guide subsequent treatment strategy[6, 7]. Thus, the gene profile post Osimertinib 1L treatment in tissue and plasma may help to guide the following treatment.

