**Table 11 Panel list of NGS**

ABL1	FANCC	NFKBIA	TP53	CBR1	EIF4A2	HIST1H2AC	MCC	PLCG2	SMC1B	XPC
ACVR1B	FANCD2	NKX2-1	TSC1	CBR3	EIF4G3	HIST1H2AG	MCM3	PLK1	SNCAIP	XRCC1
AKT1	FANCE	NOTCH1	TSC2	CCDC168	ELAC2	HIST1H2AL	MDC1	PLXNA1	SNTG1	XRCC3
AKT2	FANCF	NOTCH2	TSHR	CCNA1	ELF1	HIST1H2AM	MECOM	PLXNB2	SNX29	YAP1

AKT3	FANCG	NOTCH3	U2AF1	CCNB3	ELF3	HIST1H2BC	MEF2C	PNRC1	SOD2	YY1AP1
ALK	FANCL	NPM1	VEGFA	CCT3	ELMO1	HIST1H2BD	MGA	POLQ	SOS1	ZBTB16
APC	FANCM	NRAS	VHL	CCT5	ELN	HIST1H2BJ	MIB1	POM121	SOX10	ZC3H11A
AR	FAS	NSD1	WRN	CCT6B	EME2	HIST1H2BK	MIOS	POM121L12	SOX17	ZFHX3
ARAF	FAT1	NTHL1	WT1	CD22	EMID2	HIST1H2BO	MKL1	POU2AF1	SPEN	ZFP36L1
ARID1A	FAT2	NTRK1	XPO1	CD33	EML4	HIST1H3B	MLL4	PPM1D	SPRR3	ZFP36L2
ARID1B	FBXW7	NTRK2	XRCC2	CD5L	EPC1	HIST1H3C	MLLT3	PPP1R17	SPSB4	ZFPM2
ARID2	FGF19	NTRK3	ZMAT3	CD74	EPHA1	HIST1H3D	MMP11	PPP6C	SPTA1	ZIC3
ASXL1	FGF3	PALB2	ABCA13	CDA	EPHA4	HIST1H3F	MMP2	PRDM16	SRD5A2	ZNF217
ATM	FGF4	PARK2	ABCB1	CDH11	EPHA7	HIST1H3G	MN1	PREX2	SRGAP1	ZNF384
ATR	FGFR1	PARP1	ABCC1	CDH18	EPHB2	HIST1H3H	MNDA	PRF1	SRGAP3	ZNF521
ATRX	FGFR2	PAX5	ABCC11	CDH23	EPHB4	HIST1H3I	MNX1	PRKAA1	SRSF2	ZNF638
AURKA	FGFR3	PBRM1	ABCC2	CDK13	EPOR	HIST1H4I	MSH4	PRKCB	SRSF7	ZNF750
AURKB	FGFR4	PCK1	ABCG2	CHD1	EPPK1	HIST3H3	MSN	PRKCI	STAG1	ZNF804B
AXIN1	FH	PDCD1	ABL2	CHD1L	EPS15	HLF	MSR1	PRKDC	STAT1	HLA-A
AXIN2	FLCN	PDCD1LG2	ACACA	CHD4	ERBB2IP	HMCN1	MTHFR	PRRX1	SUCLG1	HLA-B
AXL	FLT1	PDGFRA	ACIN1	CHD6	ERCC2	HNF1B	MTRR	PRX	SUCLG2	HLA-C
B2M	FLT3	PDGFRB	ACTB	CHD8	ESR2	HNRPDL	MUC5B	PSG2	SULT1A1	
BAP1	FLT4	PDK1	ACTG1	CHD9	ETS1	HOXA11	MYH11	PSIP1	SUZ12	
BARD1	FOXA1	PIK3CA	ACTG2	CHFR	ETV1	HOXA13	MYH14	PSMB1	SVEP1	
BCL2	FOXL2	PIK3CB	ACVR2A	CHI3L1	ETV5	HOXA3	MYH9	PSMB5	SYNCRIP	
BCL2L1	FOXP1	PIK3CG	ACVRL1	CHN1	ETV6	HOXA9	MYO3A	PTGS1	SYNE1	
BCOR	FUBP1	PIK3R1	ADAM29	CIITA	EWSR1	HOXC13	MYOD1	PTGS2	TAF1	
BLM	GALNT12	PIK3R2	ADAMTS5	CLDN18	EZR	HOXD11	NAP1L1	PTPN13	TAF15	
BMPR1A	GATA3	PMS1	ADCY1	CLP1	F8	HOXD13	NAV3	PTPN2	TAF1L	
BRAF	GNA11	PMS2	AFF1	CLSPN	FAM131B	HSD3B1	NCAM2	PTPRB	TAL1	

BRCA1	GNAQ	POLD1	AFF2	CLTC	FAM135B	HSP90AA1	NCF2	PTPRK	TBL1XR1
BRCA2	GNAS	POLE	AFF3	CNOT3	FAM157B	HSP90AB1	NCF4	PTPRO	TBX15
BRD4	GRIN2A	POT1	AHNAK	CNOT4	FAM46C	HSPA8	NCK1	PTPRS	TBX22
BRIP1	GRM3	PPP2R1A	AKAP9	CNTN1	FAM5C	HSPD1	NCOA3	PTPRT	TCEB1
BTK	HDAC1	PRDM1	ALB	CNTN5	FAP	HSPH1	NCOA4	PTPRU	TCF12
CARD11	HGF	PRKAR1A	AMOT	CNTNAP1	FASLG	ICK	NCOR2	RAB35	TCF3
CASP8	HNF1A	PTCH1	ANGPT1	CNTNAP5	FAT3	ICOSLG	NCSTN	RAC2	TCF4
CBFB	HOXB13	PTCH2	ANK3	COL1A1	FAT4	ID3	NDUFA13	RAD21	TCL1A

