4.2.2 Primary outcome(s)

Gene profile in tissue

Gene profile is defined as gene alteration detected by NGS and frequency of every gene alteration. All gene alterations include gene mutation, copy number variation(CNV), fusion, etc.

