4.2.3 Secondary outcome(s)

Gene profile in plasma

Gene profile is defined as gene alteration detected by NGS and frequency of every gene alteration.

[figure not shown]
Proportion of Gene X alteration(%) = (number of patients with Gene X alteration, which is an example of a certain gene)/(total number of patients in the FAS)×100%.

Concordance of plasma and tissue

Using selected representative genes (for example EGFR, MET, PIK3CA and etc.) to measure the concordance of plasma and tissue mutation for each gene. Concordance of Gene X in plasma and tissue is defined as sensitivity, specificity, positive predictive value (PPV) and negative predictive value (NPV) between plasma and tissue results.

The percentage of pathology transformation

Pathology transformation is defined as those transformation from non-small-cell lung cancer to small-cell lung cancer or from adenocarcinoma to squamous carcinoma, can be observed by IHC.

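### SAP 5.4.2 picks the concordance genes by their frequency in tissue, the reference sample, and fixes no named alterations: plasma PPV is biased upward and an NGS result for MET amplification is not assured

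*SAP*

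**What the plan says.** SAP 5.4.2 (Secondary Endpoint) sets the rule: "The representative genes should include the top 20 mutated genes observed in tissue samples". The same section states: "Tissue sample is the reference standard". It names no gene.

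SAP 4.2.3 gives genes only as examples, and its unit is mutation by gene: "Using selected representative genes (for example EGFR, MET, PIK3CA and etc.) to measure the concordance of plasma and tissue mutation for each gene". SAP 4.2.2 is wider for the gene profile: "All gene alterations include gene mutation, copy number variation(CNV), fusion, etc". Nothing says whether copy-number gains or fusions count when genes are ranked as mutated, or whether MET amplification is scored apart from MET mutation.

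PPV in SAP 5.4.2 is "number of patients with positive result in both plasma and tissue)/(total number of patients with positive result in plasma samples", so it depends on how common the alteration is in tissue.

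Protocol 8.3.2.2.2 contains no top-20 rule. The SAP's section on changes to protocol planned analyses lists only the addition of overall percent agreement.

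Protocol 4.2.1 gives the purpose, which is to learn whether plasma can stand in for tissue when biopsy is not possible. Its one criterion is a point estimate of sensitivity of at least 80%.

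**The concern.** The reference result chooses the genes on which plasma is then judged, in the same patients. A gene whose tissue count is high partly by chance is more likely to be chosen. Its plasma positives then look better confirmed than they would in new patients.

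The rule also works on genes, while the clinical question concerns particular resistance alterations. The protocol's rationale names MET amplification and EGFR C797, L792 and G724, and Protocol 2.2 says that plasma sensitivity for copy-number change is unstable. Every participant had ex19del or L858R before osimertinib (Protocol 5.1, criterion 4). A patient positive for the founder mutation in both samples therefore counts as concordant for EGFR, even if C797X is seen in only one of them.

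The study could thus report an optimistic PPV for frequent genes and have no required NGS result for the alterations that motivate it.

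**Working it through.** **The plan's own figures.** The documents give none for concordance or for the number of genes. Those they do give reproduce. At 20% incidence and n = 200 the Clopper-Pearson interval is 14.7% to 26.2%. The chance of at least one case at 1% is 1 − 0.99^200 = 86.6% (stated as 86%). Evaluable pairs are 200 × 0.90 = 180.

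**Inputs from the documents.** Evaluable pairs, 180 (SAP 2.2). Interim, about 100 (SAP, timing of all analyses). Sensitivity, 80% (Protocol 4.2.1). Plasma assay specificity, above 95% (Appendix F, Table 10). Panel of about 1,000 genes (Table 11). MET amplification, 15% in a plasma series of 91 and 7% in a tissue series of 27 (Protocol 1.1, Rationale).

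**Assumptions.** The documents give no gene-frequency spectrum, so every spectrum below is assumed. So are the alternative plasma performance values: specificity 99%, or sensitivity 60% with a 2% plasma-only rate.

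**Step 1: PPV and prevalence.** PPV = Se·p / [Se·p + (1 − Sp)(1 − p)]. With Se 80% and Sp 95%, p = 1%, 5%, 10%, 20% and 50% give 14%, 46%, 64%, 80% and 94%. Ranking by tissue frequency therefore selects genes whose true PPV is high. That limits scope; it is not itself a bias.

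**Step 2: selection bias.** Simulate tissue and plasma results, rank by tissue count, keep 20 genes, and compare observed with true PPV for those genes at n = 180.

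| Assumed spectrum | Plasma performance | Average PPV bias, points |
|---|---|---|
| 200 genes at 5% | Se 60%, plasma-only 2% | 61% true, 73% observed: +12 |
| 200 genes at 3% | same | 48% true, 64% observed: +16 |
| all genes at 5% | Se 80%, Sp 95% or 99% | +13 or +7 |
| frequent genes plus a long tail (200 genes from 5% to 0.5%, or 1,000 from 4% to 0.2%) | Se 80%, Sp 95% to 99% | +4 to +8; ranks 16-20, +6 to +14 |
| frequency declining with rank | Se 60%, plasma-only 2% | +2 to +5; ranks 16-20, +6 to +8 |

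For the first row, true PPV = 0.05 × 0.6 / (0.05 × 0.6 + 0.95 × 0.02) = 61%. At the interim (n = 100), observed PPV in the first two rows rises to 76% and 69%, and the bias in the fourth is +6 to +13. Bias in sensitivity and specificity is at most 0.2 point at n = 180.

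**Step 3: does MET enter the top 20 at n = 180?**

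| MET alteration counted | Chance of entry |
|---|---|
| Amplification at 15% | 92% with 25 other genes at 8-20%; about 96-100% otherwise |
| Amplification at 7%, 200 other genes at 3%, 5% or 8% | about 88%, 44% or 3% |
| Amplification at 7%, frequent genes plus long tail | 78% to 85% |
| Amplification at 7%, frequency declining with rank | up to about 97% |
| Amplification at 7%, 25 other genes at 8-20% | 2% |
| MET mutations only, assumed 1% to 3%, long-tail spectra | 0% to 6% |

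**Step 4: precision with a fixed list.** MET amplification at 7% to 15% of 180 gives about 13 to 27 tissue positives. The exact 95% interval for sensitivity is 46% to 95% for 10/13 and 62% to 94% for 22/27.

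**The case against.** The other side has four good arguments.

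- The rule is written in advance, and only the gene identities depend on the data. A reader might infer that genes are hand-picked after the results; the documents do not support that.
- The wording sets a minimum. A reader might infer that genes seen mainly in plasma are barred. They are not: they may be added, and the full plasma profile is its own secondary endpoint. They simply cannot qualify through the ranking.
- The criterion on which plasma is judged is sensitivity, which selection on tissue leaves unbiased. PPV carries no threshold. The PPV bias therefore does not undermine the 80% criterion.
- Flat spectra are close to a worst case, because ranking is then pure noise. A steep geometric decline from 60% leaves only about +0.5 point.

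On MET, the SAP's definition of alterations includes copy-number change, so reading the ranking as mutations only is one reading of loose wording. Protocol 2.2 and 7.3.2 also plan a comparison of tissue FISH with blood ddPCR. It is exploratory, covers about 80-100 samples if tissue suffices, and is not NGS. Redacted text may say more.

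All of this stands, and it limits the size of the point. It does not supply a required NGS result for MET amplification or for the EGFR resistance mutations.

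**Conclusion.** The point holds as an inexpensive improvement to a secondary analysis. The direction of the PPV bias follows from selecting on the reference. Its size rests on assumed spectra: about +2 to +16 points on average at 180 pairs, close to zero if frequencies fall steeply, and larger at the interim.

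A reader might infer that MET amplification will be left out. The documents do not show that. At 15%, with copy-number gain counted, it almost always enters. At 7%, or if only mutations count, the plan gives no assurance. That gene-level EGFR says little about resistance mutations follows from the eligibility criterion, on the expectation that the founder mutation is still detectable in nearly all tissue samples, which would leave few tissue negatives.

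**What to change.** In SAP 5.4.2, before tissue results are tabulated and at latest before database lock:

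1. Fix an alteration-level concordance list from what the protocol names: MET amplification scored apart from MET mutation; EGFR C797X, L792 and G724; and PIK3CA.
2. Keep the top 20 as a descriptive table on all pairs. State that copy-number change and fusion count in the ranking. Either note that its PPV is optimistic, or rank on tissue and plasma positives together.
3. List the top-20 rule under changes to protocol planned analyses.

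Ranking on the interim patients and estimating on the rest is not worth its price, since it would leave about 180 − 100 = 80 pairs.

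The cost is SAP wording and one extra table. The downside is few positives and wide intervals for the rarer named alterations, as the 10/13 example shows.
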